Microbiome and Innate Immunity with Percutaneous Osseointegrated Prostheses

Protocol Summary

IRB Approval Date of Current Version:	7/12/2019	
University of Utah IRB #:	IRB_00073178	
Sponsor:	VA REHABILITATION RESEARCH AND DVLPMNT	
Principal Investigator:	[name]	
Internal Staff and Sub-Investigators:	Site Name	Staff Names
	Veterans Affairs SLC Health Care System (VAMC)	[name] [name] [name] [name]

This document was created using the ERICA Online System at the University of Utah. The document is created from study information approved by the IRB on the date listed above. Any alteration to the original content of this document may not be considered to represent the study as approved by the IRB.

Background and Introduction

Percutaneous osseointegrated prosthetic attachment (i.e., the direct skeletal attachment of artificial limbs) is a rapidly evolving technology that is now ready to be introduced into the United States. This follows over a decade of European trials that largely involved transfemoral amputees. Translational animal research carried out over the past seven years at the VA, Salt Lake City, Utah, has clarified principles of osseointegration, and bone and skin interface responses to chronic weight bearing on a skeletally attached artificial limb. This information has produced new prosthetic designs that make the technique safer and more likely to succeed over the long-term. This translational animal data, gathered in parallel to the European human data, has made it possible to commence an Early Feasibility Device Exemption (IDE) Pilot Program under the direction of the FDA. This trial is anticipated to begin October 19, 2015, at the VAH in Salt Lake City, Utah, and is funded by VA RR&D grant (RX001208-01). Ten transfemoral amputees, selected from the veteran and active military populations will receive a PODS device.

The critical limiting factor to the prior U.S. introduction of this technology has been an up to 30% infection rate at the implant/skin interface in European patients. Evolving designs and surgical techniques have lowered this incidence, but it remains remarkable that 70% to perhaps 95% of European patients now remain infection free by simply using mild soap and shower hygiene at the stoma, and avoiding the use of antibiotics. In fact antibiotics and disinfectants have been found to be counter productive and lead to antibiotic resistance. It is increasingly evident that the key to this improbable success is the biology and presence of a mutualistic-commensal microbiota at the skin/implant interface. These “good bacteria” are the “guard dogs at the gate”.

Microbiome studies: Traditionally, wound microbiotas have been characterized by culture based assays. Cultures, however, account for only 3% of the bacterial strains actually present. A recent study, reported that, on average, culturing techniques underestimated microbial load by 2.34 logs ($P < 0.0001$), and in some cases greater than 6 logs. Bacterial cultures, because they are designed to select for specific pathogens, are unable to grow and recognize most of the other resident skin microbiota. These non-molecular techniques do not allow a full understanding of the complexity of stomal colonization in both the diseased and healthy states.

The relationships between the bacterial subsets within an ecological community are complex. There is strong evidence to suggest that microbes that are commonly thought of as pathogens can live commensally on the skin. In fact, bacteria from the genera *Staphylococcus*, *Corynebacterium*, *Propionibacterium*, *Streptococcus* and *Pseudomonas*, may directly benefit the host (mutualism) and only rarely will they become pathogens. Recent developments in molecular based technology have now paved the way to more advanced genome based techniques for identifying bacterial ecologies (microbiome). Techniques based upon distinct bacterial molecular markers, such as 16S rRNA are now being employed to truly understand the complexity and complicity of the human microbiome.

Inflammatory biomarkers: Wound healing involves a complex process with many overlapping stages: coagulation, inflammation, cell proliferation and migration, and finally tissue remodeling with wound closure within 3-14 days. However, as a result of our percutaneously implanted device, we expect the area around the stoma of our patients to

evidence a chronic/continuous wound healing process. Understanding the relationship between the microbiome and modulating the cycle of inflammation produced by microbial colonization and/or infection is a critical step towards improving treatment strategies.

We postulate that comparing the profiles of local and systemic inflammatory biomarkers can provide valuable information regarding the state of health of the skin surrounding the implant. Because different cytokines can have overlapping biological functions, as well as regulate production of other cytokines, the ability to simultaneously analyze a large set of cytokines within a localized environment (such as a site of inflammation) can be more valuable than detecting the levels of individual cytokines (particularly if only small volume test samples are obtained). Collecting multiple samples over time will also allow for longitudinal studies of cytokine profiles within a single patient.

Biomarkers (e.g., cytokines and chemokines) are proteins that act as effectors or modulators of the inflammatory response. Custom TaqMan microfluid array cards (assaying 192 genes) will be able to detect mRNA expression patterns of systemic inflammatory proteins. These can then be compared to native secreted proteins locally present at the implant site: the latter detected using the Bio-Plex multiplex immunoassay system measuring 27 cytokines.

The biomarkers detected in this study (using the Bio-Plex system) outperformed the erythrocyte sedimentation rate (ESR) and the C-reactive protein (CRP); tests that are commonly used in standard clinical practice to detect the presence of infection. We therefore believe that in addition to having a better understanding of the cytokine profile expected of a chronic wound in a stable state (when compared to an infected state) it is possible that a diagnostic cytokine profile may be determined that will predict the onset or detect the presence of a subclinical infection.

Purpose and Objectives

Purpose

The purpose of this study is to investigate the clinical implementation of a new percutaneous prosthetic attachment system (Safety Study of Percutaneous Osseointegrated Implants for Prosthetic Attachment; separate IRB # 00082763) by determining the resident microbial ecology of the implant exit site and to simultaneously study the systemic and local stomal immune responses. We will use two, state-of-the-art, pre- and post-surgery bacterial monitoring technologies: these procedures are intended to facilitate the early prediction, detection, and treatment of infection, as well as to provide follow-up data that can potentially be used to advantageously manipulate the stomal microbial environment in future clinical trials.

Objectives

The objective of this study is to follow 10 patients implanted with a percutaneous osseointegrated exoprosthetic docking system (PODS) for a period of one year. This PODS

technology requires invasive surgery to skeletally attach a metal implant, which protrudes from the long bone and exits the stump skin of the amputee patient (IRB# 00082763, as above). All stomas are colonized by local skin bacteria; colonization does not necessarily result in infection. Over time, the presence of this skin penetrating foreign object (implant) will cause measurable changes in the bacterial population (microbiota) at and around the PODS exit site.

It is anticipated that the evolving microbiota, in concert with measurable changes in the local and systemic cytokine responses, will reveal patterns associated with mutualistic-commensal bacteria and/or pathogenic bacteria related to the stages of chronic wound healing. These patterns could be used to determine the presence of a stable uninfected stoma or the progression of a stomal infection. Hopefully, this information will allow timely intervention to prevent infection, i.e. by detecting early stages of infection or discerning common patterns of stable mutualistic-commensal bacterial strains, effective intervention protocols (antibiotics, probiotics or manipulation of the stomal and skin microbiota) may be developed to avoid patient morbidity and assure implant survival.

The study aims will test the following:

Aim 1: Determine and characterize the microbiota in the region surrounding the skin/implant interface. Sampling will take place over all stages of wound healing and stomal maturation and will begin with Stage 1 and Stage 2 surgeries, as well as at defined time points, and collection sites (i.e., the stoma, ipsilateral and contralateral thigh skin) for up to one year post surgery. This will be carried-out by using a specific swabbing technique to collect bacterial DNA and to amplify and sequence bacterial 16S rRNA genes.

AIM 2: Compare the expression patterns of the local and systemic inflammatory biomarkers over time and determine if there is a correlation with the microbiota pattern to diagnose the state of wound healing at the skin/implant interface and the systemic response to a potentially life-long chronic wound. The measurements of the pro-inflammatory cytokines, found in the stomal exudate (local biomarkers) and blood serum (systemic biomarkers), along with evolving microbiota profiles (Aim #1) will help to better characterize the homeostatic state of the stoma and subsequent optimum wound care therapies.

The ability to predict infection and to avoid it without the use of antibiotics would be of great value to future clinical trials. Assuming the success of this feasibility pilot trial, it is anticipated that the trial will be expanded to include 200 patients.

Study Population

Age of Participants: 18-70 years old

Sample Size:

At Utah: 10
All Centers: 10

Inclusion Criteria:

Only participants enrolled in IRB #00082763 study will be enrolled in this study. For the IRB study #00082763 study, participants come from a pool of subjects who are veterans and have transfemoral limb loss that is not a result of dysvascular disease. These patients are considered to be capable of functioning with socket suspension transfemoral prostheses but are also suitable for fitting with a percutaneous implant system.

Inclusion criteria for # IRB 00082763 are:

A potential subject will be included in the study if he or she meets all of the following inclusion criteria:

1. Is a US military veteran with transfemoral limb loss, that occurred at least 6 months prior to consent, and that the amputation is not a result of dysvascular disease.
2. Is at least 18 years of age or older.
3. Has previously used or is currently using a “socket suspension technology” prosthesis
4. Has, in the opinion of the investigator, normal cognitive function and no physical limitations, addictive diseases, or underlying medical conditions including tobacco use (continued testing for tobacco use will be performed at screening) that may prevent the subject from being an appropriate study candidate.
5. Is willing, able, and committed to participation in baseline and follow-up evaluations for the entire duration of the study.
6. Can provide written informed consent to participate.

Exclusion Criteria:

A potential subject will be excluded from study participation if he/she meets any of the following criteria (the IRB 00082763 study criteria)

1. Is currently on active or reserve military duty
2. Has experienced systemic bacterial infection or localized infection at the stump site within the previous 6 months
3. Has had more than 1 limb amputated
4. Has a body mass index (BMI) ≥ 30
5. Has insulin dependent diabetes mellitus (IDDM) or has adult onset DM with a glycated hemoglobin (HbA_{1c}) > 53 mmol/mol (7.0%) at screening

6. Has residual femur bone length of less than 25% of the length of the contralateral femur.
7. Has clinically diagnosed vascular compromise proximal to the surgical site
8. Is pregnant at the time of surgery or plans to become pregnant within the first year of follow-up
9. Has evidence of recent tobacco use (urine cotinine test > 300 ng/mL [1703 nmol/L]) and is not committed to a smoking-cessation program
10. Has renal insufficiency (defined as serum creatinine of \geq 1.8 mg/dL) or is currently receiving renal dialysis
11. Is currently involved in or plans to be involved in high levels of physical activity (competitive sports, heavy physical labor, etc) during the first 12 months of the rehabilitation stage
12. Has muscular, neurologic or vascular deficiencies that may compromise the bone or soft tissue healing of the affected extremity
13. Has anemia characterized by a hemoglobin of \leq 11 g/dL at the time of surgery
14. Is currently on oral anticoagulation (excluding low-dose aspirin for cardiac prophylaxis)

Design

Other

Retrospective sample analyses

Study Procedures

Recruitment/Participant Identification Process:

Only patients, who will be recruited and consented to participate in IRB#00082763 study, will participate in this "Microbiome" study to retrospectively assess the progression of wound and stomal healing and/or the occurrence of infection, as a safety survey and previously described.

Informed Consent:

Description of location(s) where consent will be obtained:

George E Wahlen Department of Veterans Affairs Hospital, Salt Lake City Health Care System.

Description of the consent process(es), including the timing of consent:

Consent process is now part of the IRB study # 00082763. No separate consent process will be used.

Requested Waivers/Alterations of Consent:

Waiver of Informed Consent VA Waiver of Consent for Recruitment Purposes Only

Procedures:

-Patient selection

All patients selected to participate in the "Safety Study of Percutaneous Osseointegrated Implants for Prosthetic Attachment (IRB #00082763)" will participate in this study. As this is safety evaluation study, subjects will not be randomized. Follow-up end point will be 1 year post 2nd stage surgery.

Patients will be consented through IRB study # 00082763.

- Obtaining consent

Patients are consented as part of the IRB #00082763 consenting process

- Sample collection

Samples (skin swabs, tissue and blood) for this study will come from the samples collected and tissue-banked as part of the IRB # 00082763.

Collection process is described in IRB # 00082763. Briefly, samples will be collected from each patients at different pre- and post-operative time points (see below).

Pre-op stage 1/day of the procedure, 3+/-7 days of stage 1 post-op, pre-op of stage 2/day of procedure, day 7 +/- 7 days of stage 2, 2 wk +/- 14 days of Stage 2, and 6wk +/- 14 days, 3, 6,9, 12 mo +/- 30 Days of stage 2.

-Analysis

-Reporting

Procedures performed for research purposes only:

Statistical Methods, Data Analysis and Interpretation

Statistical analysis: A sample size of n=10 patients is planned to be used.

Sample Size Justification. A sample size of n=10 patients will be used. Even if the specific comparisons, which involve a single predictor variable, described for Aims 1 to 3 reveal trends that are not statistically significant, it would be sufficient to show that overall model fit is significant. That is, a significant multivariable curvilinear correlation with pro-inflammatory cytokines, for example, would demonstrate that Bio-Plex array is potentially a sensitive indicator of inflammation and/or infection, provided that a visible shift in the graphed growth curve occurs

with the onset of inflammation and/or infection. With a sample size of 10, there is 80% power using a two-sided alpha 0.05 comparison, to detect a correlation of $r=0.71$ or greater. Converting this to a coefficient of determination, $r^2 = 0.50$, the multivariable model would have to account for 50% of the variability in pro-inflammatory cytokines concentration. Since cytokines is measurable, going up or down across healing time in an anticipated fashion, with time being one of the predictor variables making up the multivariable curvilinear correlation, it is reasonable to assume that this magnitude of correlation will be observed in this study. Furthermore, the repeated measurements increase the statistical power somewhat. The study, then, is adequately powered to demonstrate the feasibility of microbiota, and pro-inflammatory cytokines/markers as indicators of inflammation and/or infection.

Microbiota analysis

In this microbiota study, the temporal dynamics of the stomal bacterial ecology of these ten patients were investigated over the duration of one-year following the second surgery. skin swab samples were collected at regular intervals using swabs obtained from 3 different sites. Pre-surgery data was used as a baseline, thus, each patient had their internal control, and the microbiota changes to the individual patient's pre- and post- skin swab samples were compared. The DNA extraction were performed using the standard procedure. The 16S ribosomal RNA genes were amplified using broad range PCR primers targeted to the V1-V3 hypervariable region (V1V3 Forward primer 5'-AGAGTTTGATCCTGGCTCAG-3' and V1V3 Reverse primer 5-ATTACCGCGGCTGCTGG-3'), with barcodes unique to each sample. PCR reactions were carried out in quadruplicate using high fidelity Accuprime Taq. The resulting 16S rDNA amplicons were purified using a 1:1 volume of SPRI beads, quantified using PicoGreen, pooled in equal amounts, and sequenced on the Illumina MiSeq using 2x300 bp chemistry. Extraction blanks and DNA-free water were subjected to the same amplification and purification procedure to allow for empirical assessment of environmental and reagent contamination. Sequencing was performed by the PennCHOP Microbiome Center on the Illumina MiSeq instrument. Sequencing results were then processed using the hmmUFOtu workflow. Reads were demultiplexed using the prior mentioned barcodes. Individual reads (with $\geq 97\%$ identity) were treated as same species sequences, and were clustered and assigned to operational taxonomic units (OTUs) using the Greengenes 13_8 database. OTUs that were found to represent just one sequence in one sample were also removed. Any reads assigned to Cyanobacteria, a common contaminant, were also removed. OTU tables and phylogenetic trees output from hmmUFOtu were then further analyzed using the phyloseq package in R. This analysis included rarefaction of samples down to an even depth of ~ 1000 sequences per sample. Alpha and beta diversity metrics were computed using the vegan package.

All statistical analysis was performed in R. For testing statistically significant differences between populations, the nonparametric Wilcoxon rank-sum test was used (wilcox.test function in R). Due to the sample losses from rarefaction, the

unpaired test was used. Multiple testing correction was also applied with the `p.adjust` function, using the false discovery rate correction. For differential abundance testing, the DESeq2 and phyloseq packages were used with default settings. Sample similarity was calculated using the Weighted UniFrac, Unweighted UniFrac, and Bray Curtis Beta diversity metrics, and/or statistical comparisons of community composition. The Adonis function (PERMANOVA test), from the vegan package was applied to each of the aforementioned metrics. Dirichlet multinomial mixture modelling was performed using the DirichletMultinomial package. Ordination was performed using the labdsv package.

Whole Blood RNA expression data

Whole-blood samples were collected from these patients at the following time points: pre-surgery 1 (PrS1), post-surgery 1 (PoS1), pre-surgery 2 (PrS2), post-surgery 2 week 1 (PoS2-W1), post-surgery 2 week 2 (PoS2-W2), post-surgery 2 month 1 (PoS2-M1), post-surgery 2 month 3 (PoS2-M3), post-surgery 2 month 6 (PoS2-M6), post-surgery 2 month 9 (PoS2-M9), and post-surgery 2 month 12 (PoS2-M12). Whole-blood RNAs were isolated and undergone complete RNA sequencing, where single-end base pair sequencing was performed at the University of Utah Core genomic facility. Gene read counts were quantified via featureCounts and differential gene expression (DEG) analysis was performed using DESeq2.

For the DEG analysis, pair-wise comparisons were made in two sets: first, between PrS1 and all subsequent time points, second between PrS2 and all subsequent time points. Results from the DEG analysis were used to perform an enrichment analysis, which implemented topGO's elim graph algorithm paired with the Kolmogorov-Smirnov test for significance. Enrichment analysis was run on each of the Gene Ontology's (GO) sub ontologies: biological process (bp), cellular component (cc) and molecular function (mf).

References:

1. Bland, J.M. and D.G. Altman, Calculating correlation coefficients with repeated observations: Part 1--Correlation within subjects. *BMJ*, 1995. 310(6977): p. 446.
2. Bland, J.M. and D.G. Altman, Calculating correlation coefficients with repeated observations: Part 2--Correlation between subjects. *BMJ*, 1995. 310(6980): p. 633.

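### A significant overall model fit, with time among the predictors, is accepted as sufficient, but it does not test Aim 2's biomarker-microbiota correlation, and no stated analysis does

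*Combined protocol and SAP*

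**What the plan says.** Under Objectives, Aim 2 sets out to compare local (stomal exudate) and systemic (serum) biomarkers over time and "determine if there is a correlation with the microbiota pattern to diagnose the state of wound healing".

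The Sample Size Justification first allows that the single-predictor comparisons may fail to reach significance. It refers to these as belonging to Aims 1 to 3, although only two aims are listed. It then says "it would be sufficient to show that overall model fit is significant". As an example, a significant multivariable fit to cytokines would show that the Bio-Plex array is potentially a sensitive indicator, "provided that a visible shift in the graphed growth curve occurs" when inflammation and/or infection begins.

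The effect size is r=0.71 with 10 patients, so that "the multivariable model would have to account for 50% of the variability in pro-inflammatory cytokines concentration". This is called reasonable because cytokines move in an expected way during healing, "with time being one of the predictor variables making up the multivariable curvilinear correlation". No other predictor is named. The section concludes that the study is "adequately powered to demonstrate the feasibility of microbiota, and pro-inflammatory cytokines/markers as indicators of inflammation and/or infection".

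**The concern.** An overall test rejects when any predictor carries signal. The plan puts time in the model and relies on the healing trend to reach the target R². The statistical half of the rule can then be met by post-surgical change in cytokines, with no relation to the microbiota at all. Even if a microbiota variable is one of the unnamed predictors, overall fit does not isolate it. The single-predictor comparisons might have isolated it, but the rule lets them fail. The other half of the rule, the visible shift, is judged by eye, has no definition, and concerns inflammation or infection rather than microbiota.

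At stake is whether the pilot can report microbiota and cytokines as indicators without having tested the link that Aim 2 asks about. The Objectives anticipate expansion to 200 patients if the pilot succeeds.

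**Working it through.** **1. The plan's own figure.** Inputs from the Sample Size Justification: n=10, two-sided alpha 0.05, r=0.71. For one predictor with fixed values, the noncentrality is λ = n·r²/(1−r²) = 10 × 0.5041/0.4959 = 10.17. On F(1,8), with critical value 5.32, power is 79.7%, and 80% is reached at r=0.711. The stated figure reproduces as a one-predictor test.

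**2. The same figure for a multivariable model.** With R²=0.50 and n=10, λ = 10 × 0.50/0.50 = 10. The number of predictors k is an assumption, because only time is named.

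| k | Test | Critical F | Power | R² needed for 80% |
|---|---|---|---|---|
| 1 | F(1,8) | 5.32 | 79% | 0.51 |
| 2 | F(2,7) | 4.74 | 61% | 0.60 |
| 3 | F(3,6) | 4.76 | 47% | 0.68 |

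**3. What overall fit tests.** Take cytokine = b0 + b1·time + b2·time² + b3·microbiota index. The overall null is b1=b2=b3=0. Aim 2's null is b3=0. Set b3=0 and let time explain a share R² of the variance, so that λ = N·R²/(1−R²) with k=3.

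- N=10: R² of 0.10, 0.25 and 0.50 gives λ of 1.11, 3.33 and 10. The overall test is significant in 9%, 18% and 47%.
- Pooled samples: the Procedures section lists 10 sampling times, 7 of them after stage 2, so 10 patients give 100 or 70 samples. At R²=0.10, λ = 100 × 0.10/0.90 = 11.1 gives 79%, and λ = 70 × 0.10/0.90 = 7.78 gives 61%.
- Simulation, pooled without patient effects, linear time effect of 10%, intraclass correlation 0-0.5: 80-90% with 10 visits and 62-72% with 7. The microbiota term, adjusted for patient and time, was significant in 4-6%.
- If the 10% is a short post-surgical spike instead, the pooled figures are 27-36% with 10 visits and 54-62% with 7. The 10-visit result is sensitive to the assumed spike shape.

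These figures cover the statistical half only. How often the whole rule would be met cannot be computed, because the visible shift is undefined.

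**4. Whether another analysis fills the gap.**

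- Microbiota analysis: Wilcoxon rank-sum, DESeq2, PERMANOVA, Dirichlet mixtures and ordination. No cytokine variable is named.
- Whole Blood RNA expression data: comparisons between time points, then enrichment. No microbiota variable is named.
- The Background names the local measurements, "native secreted proteins locally present at the implant site: the latter detected using the Bio-Plex multiplex immunoassay system measuring 27 cytokines", but no section says how those data will be analysed.
- The References list two papers on correlation with repeated observations. The text attaches them to no analysis.

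**5. What a direct test could detect.** With patient effects, visit as a category and one microbiota index, residual df are 100−1−9−9−1 = 80, or 70−1−9−6−1 = 53. Using λ = df·ρ²/(1−ρ²) and no serial correlation, 80% power needs a within-patient correlation ρ of about 0.30 or 0.37. At the strictest FDR step for 27 cytokines (0.05/27) it needs about 0.42 or 0.50. If serum were also assayed for 27 (an assumption; 0.05/54), it needs about 0.43 or 0.52. Simulations shuffling whole patient series under one-month serial correlation of 0-0.8 gave 0.30-0.49 unadjusted and 0.44-0.64 at 0.05/27. With 20% of swabs lost, the upper ends rose to 0.54 and 0.70.

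**The case against.** The strongest reply is that the sentence claims less than it is faulted for. Its example concerns Bio-Plex as a possible indicator of inflammation or infection, is hedged, requires the visible shift as well, and sits in a feasibility justification. That stands: the plan does not say that overall fit proves a cytokine-microbiota correlation. But the rule refers to the comparisons for all the aims, and the closing sentence names microbiota as an indicator. Aim 2 is thus in scope and has no other stated test.

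A reader might infer that the healing trend makes success nearly automatic. The documents do not support this. The high percentages require pooling 70-100 samples without patient effects, which the plan does not state. It powers on 10 patients, says repeated measurements help only somewhat, and speaks of growth curves. With 10 observations the figures in step 3 are much lower.

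A reader might also infer that no linking test was ever intended. The reference to Aims 1 to 3 and the two unused references suggest that one may have been. Nor would a low infection rate show that the graphical condition could not be met, because it covers inflammation as well as infection.

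**Conclusion.** The concern holds in limited form and should be fixed. As written, a significant overall fit can arise from post-surgical change alone, so it does not address Aim 2's correlation, and no stated analysis does. This follows from the text and needs no simulation.

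The size of the problem is uncertain because the model is unstated: about 9% with 10 observations against about 60-90% with naive pooling, for three assumed predictors and a linear time effect explaining 10% of variance. The 80% power figure is correct for one predictor but is attached to a multivariable model. With two or three predictors it would be 61% or 47%.

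**What to change.** - Remove overall fit as sufficient evidence for the indicator claim and report it descriptively.
- For Aim 2, state one exploratory within-patient analysis: log biomarker on patient, visit as a category, and one microbiota index named in advance, for example stomal alpha diversity. Label it post hoc if the microbiota results are already known. The Design section reads "Retrospective sample analyses" and the Microbiota analysis section is in the past tense, so they may be.
- Test the microbiota term with a method that allows for serial correlation within patients, such as AR(1) residuals or shuffling whole patient series, and name one as primary. In simulations with one-month serial correlation of 0.3-0.8, an ordinary partial F test gave false positives of 9-21% with 10 visits and 7-16% with 7.
- Cover both exudate and serum biomarkers, with FDR control across all biomarkers tested.
- Restate the power sentence as a one-predictor figure. Give the detectable within-patient correlation: roughly 0.3-0.5 unadjusted and 0.4-0.6 at the strictest FDR step, higher with lost samples.
- Limit the inflammation or infection conclusion to a patient-by-patient description, with onset and shift defined in writing.

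The cost is SAP wording and somewhat more analysis work, with no new samples. The team must confirm which visits have cytokine data. The downside is that the indicator claim becomes harder to meet and remains exploratory.

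### No stated analysis uses infection status, and the success rule lets post-surgical inflammation alone support a claim about infection indicators

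*Combined protocol and SAP*

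**What the plan says.** The Purpose section says the monitoring is meant to help predict, detect and treat infection early. The Objectives section says of the microbiota and cytokine patterns: "These patterns could be used to determine the presence of a stable uninfected stoma or the progression of a stomal infection".

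The success rule is in the Sample Size Justification and has two parts.

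- Even if the single-predictor comparisons show only non-significant trends, "it would be sufficient to show that overall model fit is significant".
- Such a fit "would demonstrate that Bio-Plex array is potentially a sensitive indicator of inflammation and/or infection, provided that a visible shift in the graphed growth curve occurs". The sentence continues by placing the shift at the start of inflammation, infection or both.

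The same section expects the correlation to arise because cytokines move over healing time, with time as one predictor. It concludes that the study has enough power to show that microbiota and cytokines are feasible as indicators of inflammation and/or infection.

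Two contrasts have both sides stated:

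- Microbiota analysis: "the microbiota changes to the individual patient's pre- and post- skin swab samples were compared".
- Whole Blood RNA expression data: pairwise comparisons "first, between PrS1 and all subsequent time points, second between PrS2 and all subsequent time points".

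On how often infection occurs, the Background cites European rates of up to 30% and says that "70% to perhaps 95% of European patients now remain infection free".

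**The concern.** To show that a marker indicates infection, samples from infected stomas must be set against samples from infection-free stomas at a similar point in healing. The stated contrasts set one visit against another. Each patient has a Stage 1 and a Stage 2 operation, and the Background expects a continuing wound-healing process around the stoma. Cytokines can therefore be expected to move after surgery whether or not anyone becomes infected.

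The success rule does not separate the two causes. A significant fit can come from time since surgery, and a visible shift counts if it accompanies inflammation alone. Followed as written, the plan could report markers as feasible indicators of infection from data with no infected sample. The stake is more than wording, because Aim 2 is followed by a statement that a successful pilot is expected to grow to 200 patients.

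**Working it through.** **1. The plan's own figure.** The Sample Size Justification states: "With a sample size of 10, there is 80% power using a two-sided alpha 0.05 comparison", "to detect a correlation of $r=0.71$ or greater". For one fixed predictor and one independent value per patient:

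- noncentrality = r√n / √(1 − r²) = 0.71 × √10 / √(1 − 0.5041) = 3.19, with 8 degrees of freedom
- power = 79.7%, which reproduces the stated 80%

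This is power for a correlation with any single predictor. Healing time would serve, and infection status does not enter the calculation.

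**2. Which analyses use infection status.**

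| Analysis | What is compared | Infection status used? |
|---|---|---|
| Swabs (Microbiota analysis) | Before v after surgery, within patient | No |
| Blood RNA | PrS1 v later visits; PrS2 v later visits | No |
| Cytokine model (Sample Size Justification) | Curvilinear fit; time is the only named predictor | Not stated |
| Aim 2 | Local v systemic markers over time; correlation with microbiota | No |
| Rank-sum test (Microbiota analysis) | Populations that are not defined | Not stated |
| Three swab sites (Aim 1) | Stoma, ipsilateral and contralateral thigh | No |

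The first two rows are the only ones in the statistical section with both sides stated, and both compare time points. The document does not define infection, and it plans no estimate of sensitivity or specificity.

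**3. Can the rule be met with no infection?** The visible-shift part can, because its wording accepts inflammation alone. For the model-fit part, an illustrative simulation was run under these assumptions, none of which comes from the documents except the 10 patients and the 10 scheduled visits:

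- no infection in any patient
- 60 days between the two operations
- a marker peak after each operation, decaying with a 14-day constant
- within-patient correlation 0.3
- a within-patient curvilinear time model, 2,000 runs per scenario

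| Height of surgical peak | Runs with a significant overall fit |
|---|---|
| none | 4.7% |
| 1 SD | 44% |
| 1.5 SD | 79% |
| 2 SD | 97% |
| 3 SD | 99.9% |

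The exact percentages depend on these choices. What they show is that a surgical response alone can make the fit significant.

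**4. How many infections to expect.** From the Background, 95% to 70% infection free gives p = 5% to 30%. Taking this as each patient's one-year risk is an assumption, since no time frame is given; patients are treated as independent. With n = 10:

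- expected number = 10p = 0.5 to 3
- P(0) = (1 − p)¹⁰ = 0.95¹⁰ = 0.599, or 0.70¹⁰ = 0.028
- P(at most 1) = (1 − p)¹⁰ + 10p(1 − p)⁹ = 0.599 + 0.315 = 0.914, or 0.028 + 0.121 = 0.149

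**5. What an infection contrast could give.** With m infected patients out of 10, the smallest possible two-sided exact rank-sum p-value is 2 / C(10, m): 2/10 = 0.20 for m = 1, 2/45 = 0.044 for m = 2, and 2/120 = 0.017 for m = 3. With one infected patient, no result could reach 0.05. The contrast would have to be descriptive.

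**The case against.** The strongest defence is that the plan is modest. Aim 1 characterises the microbiota, and Aim 2 concerns the state of wound healing. Most references to predicting infection are framed as hopes or as matters for later trials, and the success statement claims only potential and feasibility. Surgical inflammation meeting an inflammation criterion is consistent with half of that claim. All this stands, but the Purpose section does name prediction and detection of infection, and the joint wording lets the infection half be claimed on evidence for the inflammation half.

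A reader might infer that every comparison in the plan is over time. The documents do not support that. Aim 2 sets local against systemic markers and correlates them with microbiota, swabs come from three sites, and the populations in the rank-sum test are undefined. The cytokine model has further predictors that are not named. The Sample Size Justification also refers to comparisons for Aims 1 to 3, while only two aims are listed.

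A reader might also infer that the study cannot say anything about infection, or that infected samples will necessarily be averaged with uninfected ones. Neither follows. Samples are serial within patients, the recruitment section says the occurrence of infection will be assessed, and the parent protocol (IRB 00082763), which was not available, may define and date infections. The supportable statement is that no stated analysis in this document is set up to show it.

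Finally, the low expected count is not certain: at 30% risk the chance of at least one infection is 97%.

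**Conclusion.** The point holds in a limited form. The contrasts stated in full compare time points, no stated analysis uses infection status, and the success rule can be satisfied by post-surgical inflammation alone while still supporting a statement about infection. Following the plan as written could therefore give an unsupported conclusion, so this is more than a missing detail.

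The size depends on the infection risk. At 5% the most likely outcome is no infection at all (60%), and at most one is nearly certain (91%). At 30% these fall to 3% and 15%, and the stated analyses would still not use the infections that occur. These figures rest on reading the European rates as one-year risks that carry over to these patients. The finding that infection status is absent from the stated analyses needs no such assumption. The change should be made; it does not call the sampling or the descriptive aims into question.

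**What to change.** 1. Split the success statement. Judge an inflammation claim and an infection claim separately, and say that a shift attributable to an operation does not count towards the infection claim.
2. Establish whether the parent study (IRB 00082763) holds dated infection events. If it does, cite its definition and classify each patient-visit as infection-free, pre-infection or infected. State the pre-infection window, bearing in mind that visit windows reach ±30 days. Assign the labels without reference to assay results where that is still possible. The laboratory and analysis sections are written in the past tense, so it may not be; if so, say so in the report.
3. Compare infected and pre-infection samples with the same patient's infection-free visits and with infection-free patients at the same nominal visit. Report these descriptively, as individual trajectories.
4. State that with 0 or 1 infection the study concludes only on the microbiota and markers of healing stomas.

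The cost is revised wording, a link to the parent-study records if they hold the dates, and some extra analysis. No new patients or samples are needed. The downside is a narrower claim if infections are few.
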